8.3.2. Safety Analyses

The safety analyses will consider AEs and SAEs according to their relationship with study treatment, as well as analytical results, deaths and the reasons for treatment discontinuations, delays and/or dose reductions.

All AEs and SAEs will be graded according to the NCI-CTCAE, v4.

8.3.3. Safety Stopping Rule

In addition to sample size considerations, a decision for early study termination due to safety issues will be taken within the initial 30 evaluable patients (regardless of the cohort), whenever any of the following occurs:

- Two or more eligible patients die due to treatment-related AEs (>5% of related deaths), or
- Ten or more patients need to discontinue PM01183 treatment within the first two cycles due to any grade 4 treatment-related AEs (NCI-CTCAE v4).

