	
or less than three patients out of 30 in Cohort B achieve an objective response, recruitment to that cohort will be stopped. About 110 evaluable patients are expected to be included finally in the three cohorts: Cohort A (BRCA+), Cohort A1 (BRCA+/PARPi), and Cohort B (unselected).
 
Safety Stopping Rule
 
In addition to sample size considerations, a decision for early study termination due to safety issues will be taken within the initial 30 evaluable patients (regardless of the cohort), whenever any of the following occurs:
 
 • Two or more eligible patients die due to treatment-related AEs (>5% of related deaths), or • Ten or more patients need to discontinue treatment within the first two cycles due to any grade 4 treatment-related AEs (NCI-CTCAE v4).

DURATION OF STUDY PERIOD (per patient)
	
Patients will be individually evaluated at scheduled visits within three study periods:
 
 • Screening: from signature of the ICF to first infusion of PM01183. • Treatment: from the first infusion of PM01183 to end of treatment (EOT). EOT is defined as 30 days after the date of PM01183 last administration, unless the patient starts a new antitumor therapy or dies within those 30 days, in which case the date of administration of this new antitumor therapy or the date of death will be considered as EOT. • Follow-up: after EOT, patients will be followed for any ongoing treatment-related AEs every four weeks until recovery to grade ≤ 1, or until symptoms stabilization whenever possible. 
Patients will be followed for at least one year after their first infusion. Those who discontinued treatment without PD will be assessed every two months during the first six months after last tumor assessment and every three months thereafter, until PD, start of other antitumor therapy, death, or study completion, whichever occurs first.
 
After documented PD or start of a new antitumor therapy, patients will be followed every six months until death or study completion, whichever occurs first (a documented phone contact will be acceptable).
 
Patients will be considered to be on-study from the signature of the clinical ICF to the end of the follow-up period (or screening failure).
 
Patients will be considered to be on-treatment from the date of first infusion until EOT.

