6.10. REPLACEMENT OF PATIENTS

Patients will be replaced if they are not evaluable for the primary endpoint of the study (ORR as per RECIST v1.1), specifically (any of the following):

- They are not eligible.
- They have not been treated or have not completed at least one PM01183 infusion.
- They are not evaluable for ORR as per RECIST v1.1 and they are not categorized as "treatment failures". Treatment failures will not be replaced and are defined as patients who:
 - Discontinue treatment due to any treatment-related toxicity before an appropriate tumor assessment has been performed, or
 - Withdraw PM01183 after more than two weeks on treatment without any formal evaluation

All replaced patients will be included in the general safety analysis, if appropriate.

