7. STUDY EVALUATIONS

7.1. EFFICACY

For patients to be evaluable for efficacy they must be eligible, have at least one complete infusion of PM01183, and either have at least one assessment (as per RECIST v1.1) or be categorized as “treatment failure”.

Antitumor activity will be assessed using RECIST v1.1, on a set of measurable lesions identified at baseline as target lesions and non-target lesions (if any) identified at baseline as non-target lesions and followed until PD by an appropriate method (contrast enhanced helical CT-scan, MRI, and/or clinical assessment).

Radiological and/or clinical (whenever appropriate) tumor assessment will be performed at baseline and every six weeks (two cycles) until Cycle 6 or evidence of PD. After Cycle 6, tumor assessment will be performed every nine weeks (three cycles) until evidence of PD. If an objective response is observed, according to RECIST v1.1, it must be confirmed by the same method at least four weeks after the date of the first documentation of response.

The date of response, the date of clinical or radiological PD, and the date of death will be registered and documented as appropriate.

A copy of the imaging tests conducted on the patients during this clinical trial may be requested by the Sponsor for evaluation. In addition, an independent radiological review committee may be set up, upon Sponsors' request, to review tumor assessment performed for all responding patients (partial or complete response) after study completion.

Patients will be categorized as “treatment failures” if they:

- Discontinue treatment due to any treatment-related toxicity before an appropriate tumor assessment has been performed, or
- Withdraw PM01183 after more than two weeks on treatment without any formal evaluation.

These data will be included as non-evaluable (NE) in the analysis of objective response as per RECIST v1.1, although these patients will not need to be replaced as they will be considered evaluable for efficacy.

BRCA1/2 germline mutation analysis

In patients included in Cohort B who respond to PM01183 treatment and whose BRCA 1/2 mutation status is unknown at study entry, an analysis will be performed in order to confirm or exclude deleterious germline BRCA 1/2 mutation. To this end, a blood sample will be collected at the time of response. If a BRCA 1/2 mutation is found in her sample then the patient will be analyzed along with patients included in Cohort A.

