7.2. SAFETY

Patients will be evaluable for safety if they received at least one partial or complete infusion of PM01183.

All adverse events (AEs) will be graded according to NCI-CTCAE v4.

The safety profile of patients will be monitored throughout the treatment and up to 30 days after the last treatment infusion (EOT) or until the date of death, whichever occurs first.

Treatment delays, dose reduction requirements, G-CSF and/or transfusions requirements, and reason for treatment discontinuation will be monitored throughout the study.

Any treatment-related AEs will be followed until recovery to grade ≤ 1 or stabilization of symptoms, whenever possible.

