## 4 PATIENTS EVALUABILITY CRITERIA

The study population will include patients with MBC histologically proven.

Analysis sets definitions:

- “All Included Patients” analysis set is defined as all patients recorded in the database who are included in the trial, independently of whether they have received the study drug or not.
- “All Treated Patients” analysis set is defined as all included patients who have received at least part of one infusion of PM01183.
- “All Evaluable Patients” analysis set is defined as all eligible patients who have at least one complete infusion of PM01183, and either have at least one assessment (as per RECIST v1.1) or have been categorized as “treatment failures”. Patients who discontinue treatment due to any treatment-related toxicity before an appropriate tumor assessment has been performed or those withdrawn after more than two weeks on treatment without any formal evaluation will be defined as “treatment failures”. These patients will be included as inevaluable for response in the analysis of objective response as per RECIST v1.1, although they will not need to be replaced as they will be considered evaluable for efficacy.
- “All Responder Patients” analysis set is defined as all evaluable patients who have had CR or PR as overall best response according to the RECIST v1.1 criteria.

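### The two-death safety trigger counts only eligible patients, so a treatment-related death in a treated patient later found ineligible need not count (minor, cheap to fix)

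*Protocol*

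**What the plan says.** Under Protocol 8.3.3, a decision to end the study early for safety "will be taken within the initial 30 evaluable patients (regardless of the cohort"), if either of two criteria is met. The first is "Two or more eligible patients die due to treatment-related AEs (>5% of related deaths"). The synopsis repeats it: "Two or more eligible patients die due to treatment-related AEs". The second criterion, ten or more discontinuations in the first two cycles for grade 4 related events, speaks only of patients and does not mention eligibility. The SAP does not restate the rule.

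Elsewhere, safety is defined by exposure. Protocol 7.2 says: "Patients will be evaluable for safety if they received at least one partial or complete infusion of PM01183". The SAP's treated set (section 4) is "all included patients who have received at least part of one infusion of PM01183". Efficacy evaluability is narrower (Protocol 7.1): "For patients to be evaluable for efficacy they must be eligible, have at least one complete infusion of PM01183".

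The protocol foresees treated patients who prove ineligible. Section 6.10 gives "They are not eligible" as a reason for replacement, and then says: "All replaced patients will be included in the general safety analysis, if appropriate". Section 6.2.2 also recognises that an entry-criteria deviation may make a patient ineligible.

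**The concern.** A drug-related death tells the sponsor about the drug's risk whether or not the patient later turns out to have breached an entry criterion. The rule nevertheless puts an eligibility filter on its fatal criterion and states none on its non-fatal one. No text explains the filter or adds the excluded deaths back.

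What is at stake is the formal trigger, not whether the death is seen. Section 8.3.3 is the only numerical safety stopping rule, and section 11.3 says that no independent monitoring board has been appointed. A numerical trigger exists so that stopping does not rest on discretion. Here, an eligibility finding made after the event could take a related death out of the count.

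**Working it through.** **The plan's own figure.** 2/30 = 6.7% and 1/30 = 3.3%, so two is the smallest number of deaths above 5% in 30 patients. The stated >5% is reproduced.

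**Who is left out.** The rule does not say which evaluability defines its 30 patients.
- If Protocol 7.1 is meant, ineligible patients lie outside the 30 altogether.
- If Protocol 7.2 is meant, they lie inside the 30, but the word eligible removes their deaths from the first criterion.

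Under both readings, a related death in an ineligible treated patient need not count.

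**Example.** Suppose 30 eligible patients and one ineligible patient are treated, with one related death in each group. Among all treated the share is 2/31 = 6.5%. The rule counts 1/30 = 3.3% and does not trigger.

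**Trigger probability.** The documents give neither a related-death rate for this population (Protocol 1.2.1.2 reports no treatment-related deaths in phase I) nor a number of ineligible treated patients. Both are therefore assumed, with equal risk in all patients. For n patients and death rate p:

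P(X ≥ 2) = 1 − (1 − p)^n − n·p·(1 − p)^(n−1)

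For n = 30 and p = 0.05: 1 − 0.2146 − 0.3389 = 0.4465. One more counted patient adds P(X = 1 of 30) × p = 0.3389 × 0.05 = 0.0169, giving 0.4634.

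| p | n = 30 | n = 31 | n = 32 | n = 35 | gain with 1 / 2 / 5 more (points) |
|---|---|---|---|---|---|
| 0.02 | 0.1205 | 0.1272 | 0.1340 | 0.1547 | 0.7 / 1.3 / 3.4 |
| 0.05 | 0.4465 | 0.4634 | 0.4800 | 0.5280 | 1.7 / 3.4 / 8.2 |
| 0.10 | 0.8163 | 0.8304 | 0.8436 | 0.8776 | 1.4 / 2.7 / 6.1 |

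The sponsor confirms eligibility before treatment (Protocol 6.4), so one or two is taken as the main range and five as an upper case.

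**The 7.2 reading.** If the ineligible patients are among the 30, the rule counts 29 or 28. At p = 0.05 the probability falls from 0.4465 to 0.4292 or 0.4117 (1.7 or 3.5 points). At p = 0.02 it falls from 0.1205 to 0.1140 or 0.1075 (0.7 or 1.3 points). The size is practically the same.

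**Does two still mean more than 5%?** 2/32 = 6.3%, 2/35 = 5.7%, 2/39 = 5.1%, 2/40 = 5.0%. The threshold stays above 5% for up to 39 treated patients.

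**The case against.** The strongest case on the other side has four parts.

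**The restriction could be deliberate.** Some entry limits were set for safety: Protocol 1.3 excludes patients over 75 or with poor performance status because of myelosuppression. A death in a patient who breached such a limit says less about risk in the intended population. If evaluable has its 7.1 meaning, numerator and denominator also match. This is a fair argument, but neither document makes it. Nor does it explain why the discontinuation criterion has no stated eligibility condition.

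**The safeguards are real.** Eligibility is confirmed before dosing (6.4). Serious events must be reported within 24 hours (11.2.2). A clinical oncologist and a pharmacovigilance member review safety continuously (11.3). This stands, and it is the main reason why the point is minor.

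**The window may have closed.** The planned start was the second quarter of 2012. SAP section 14.1 dates the amendments from November 2013 to February 2016, and the SAP's safety groups show Cohort B only at the 7 mg flat dose used before protocol version 3.0. This suggests that many patients had been treated before the current text, but the documents give no accrual figures. If the window has closed, a confirmation replaces the edit.

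**No text requires the stopping rule to use the safety population.** That is correct. A reader might infer that the protocol contradicts itself; it does not. The two populations simply differ.

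Two other stronger readings also fail. One is that deaths before the first tumor assessment are lost. Under 7.1, an eligible patient with one complete infusion who stops for related toxicity before assessment is a treatment failure and stays evaluable. The other is that the sponsor could not act on an uncounted death. Nothing in the rule prevents that.

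**Conclusion.** The point holds as a minor wording gap. As written, a related death in a treated patient later found ineligible need not count toward the two-death trigger, whichever definition of evaluable is meant. With one or two such patients, the trigger probability is lower than it would be with all treated patients counted, by roughly 0.7 to 1.3 points at a 2% related-death rate and 1.7 to 3.4 points at 5%. These sizes rest on an assumed death rate, an assumed number of ineligible patients and equal risk in both groups. The wording itself needs no assumption. The documents do not show that any such death occurred, or that one would go unnoticed.

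**What to change.** In Protocol 8.3.3 and in the synopsis, reword the start of the first criterion as: *Two or more treated patients (any partial or complete infusion, regardless of eligibility or replacement) die*. Add that the count covers all patients treated up to and including the enrolment of the 30th evaluable patient. Tying the end to enrolment matters because evaluability under 7.1 usually becomes known only at the six-week assessment. Keep the threshold at two and say that it stays at two if more than 30 are treated.

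Leave the discontinuation criterion unchanged. It does not mention eligibility, so this point gives no reason to alter it.

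If the window has already closed, the sponsor should instead confirm in writing that no related death in an ineligible treated patient was left out.

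The cost is one edit in two places and slightly more frequent triggering when the drug is safe. At a 1% related-death rate, the probability rises from 0.036 to 0.038 with 31 treated and 0.041 with 32 (0.048 with 35).

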9. PHARMACOKINETICS

PK parameters of plasma PM01183 will be evaluated immediately before and during the first two cycles with a limited sampling schedule of ten samples in at least 30 treated patients in cohorts A and B. The sampling schedule during each cycle will be as shown [Table 6](#). All sample collection dates and times will be recorded on the CRF.

The infusion rate will be predetermined to ensure that the total drug dose is infused in 60 minutes at a constant rate. In order to obtain reliable PK information, the infusion rate should not be modified once the infusion begins. If a variation in the infusion time eventually occurs, it is very important to reflect it on the CRF and PK sheet, writing clearly the time of the beginning and the end of the infusion.

Table 6. Sampling schedule for the determination of PM01183 PKs

Sample	Day	Time
# 1	1	Before infusion
# 2	1	5 min before the end of the infusion (EOI)
# 3	1	15 minutes after EOI
# 4	1	1 hour after EOI
# 5	1	2 hours after EOI
# 6	1	4 hours after EOI
# 7*	1	5 hours and 30 min after EOI
# 8**	2	24 hours after EOI
# 9***	4	72 hours after EOI
# 10****	8	168 hours after EOI

* There is a 30-minute window (before and after the stated point) in the sampling time.

** There is a two-hour window (before and after the stated point) in the sampling time.

*** There is a two-hour window before the stated point, or until 24 hours after the stated point in the sampling time (this sample must be collected within Day 4 or 5).

**** Preferred time; if weekends or other reasons make the sampling on time difficult, it may be obtained with a 24-hour window before or after the stated time. In any case, the sampling time should differ by at least 24 hours from the prior sample.

EOI, End of Infusion; h, hour(s); min, minute(s).

The accurate recording of actual dosing and sampling times is much more important than the strict adherence to the scheduled times. Therefore, as a result of information obtained

during sample evaluation, sampling times may be changed (as long as the total number and volume of samples is maintained or decreased) in order to improve the schedule.

Blood samples for PK analysis will be obtained through a peripheral vein located in the contralateral side to that of the infusion, whenever possible. In any case, the sampling vein has to be different to that in which drugs are infused. Even the last sample **must never be collected from the catheter used for drug infusion.**

If the blood sample is obtained from a catheter, the first milliliter of blood will be discarded to avoid dilution of the sample with the solution used to keep it clean. Heparin (10 U/ml in normal saline solution) or a slow drip of normal saline solution (10 ml/h) can be used to keep the catheter permeable between extractions.

A total of 20 samples of about 4 ml of whole blood will be collected along the first two cycles (about 80 ml of whole blood) at the predefined times depicted [Table 6](#). The Instruction Manual for Collection, Labeling, Storage and Shipment of Pharmacokinetic Samples describes in detail the required procedures. Please read it carefully before PK sampling. In short, after collection each sample will be centrifuged and the resulting plasma layer transferred into a new tube for the determination of PM01183 concentration. The tubes containing plasma will be stored frozen until their shipment to the Central Laboratory for Pharmacokinetic Samples (see Study Contacts). All the material for PK procedures will be provided by the Sponsors.

Once all samples from a patient's cycle have been collected, they should be shipped for analysis to the Central Laboratory for Pharmacokinetic Samples as soon as possible, ideally on the next shipping day. If the same center has samples from several patients, the samples can be sent in the same shipment. However, **the time span between the obtainment of the last PK sample from a patient and the shipment of all the samples from this patient to the Central Laboratory should not exceed one month.**

Sampling PK sheets should be sent together with the samples, but never in contact with dry ice. Samples will be identified with the following data: protocol code, drug, patient number, sample number, and date and time of collection. The confidentiality of patients' data will be maintained at all times. Samples will be destroyed following the appropriate laboratory procedures, after the approval of the final analytical study report by the Sponsors.

9.1. EVALUATION OF PHARMACOKINETICS

Pharmacokinetic parameters will be elucidated using standard non-compartmental analysis (NCA). The following parameters will be calculated: AUC, C_{max} , CL, and half-life ($t_{1/2}$).

The area under the plasma concentration-time curve (AUC_{inf}) will be determined using the log-linear trapezoidal method with extrapolation to infinity using the terminal rate constant k (C_{last}/k , where C_{last} is the last measured analyte concentration). The C_{max} will be derived directly from the experimental data. The terminal rate constant (k) will be estimated by log linear regression analysis of the terminal phase of the plasma concentration vs. time curve. The $t_{1/2}$ will be calculated from the equation $0.693/k$; total plasma CL will be determined by dividing the total administered dose by the AUC_{inf} .

If considered appropriate by the Sponsor, compartmental analysis on the study results will also be performed, and population PK analysis will be made in pooled results of the different studies. If applicable, PK/PD parameters will be correlated.

9.2. PHARMACOKINETIC STATISTICAL METHODS

PK parameters will be tabulated and selected parameters will be graphically displayed. The dose-exposure relationships for C_{max} and AUC will be evaluated.

The potential influence on selected PK parameters of selected demographic and clinical dichotomous variables (gender, laboratory test results above/below selected cut-off values, etc.) will be evaluated by Student's *t* test or Mann-Whitney's U test as appropriate.

For multinomial variables, analysis of variance will be used. For selected continuous demographic and clinical variables (age, laboratory test results, etc.), relationship with selected PK parameters will be graphically explored and assessed using correlation and regression methods.

Other tests may be applied if the results of the above evaluations suggest that they may yield additional relevant information.

10. PHARMACOGENOMIC SUBSTUDY

The main objective of the PGx study (optional for cohorts A and B, required for cohort A1) is the identification of potential biomarkers of sensitivity or resistance to PM01183 and whose expression might be predictive of the clinical outcome after treatment with PM01183.

Requirements

- PM01183-treated patients with prior paraffin-embedded tumor samples, if available.
- For cohorts A and B, patients who voluntarily sign the ICF for the PGx study will participate (refusal will not affect patient participation in the clinical study PM1183-B-003-11).
- For cohort A1, availability of a baseline (taken at any time between the end of last antitumor therapy and before first study drug infusion) tumor biopsy is also required. For those patients whose disease is not amenable to tumor biopsy, approval by the Sponsors must be requested prior to inclusion.

Potential biomarkers of PM01183 activity will be evaluated on paraffin-embedded tumor samples obtained at baseline. Additionally, if archived tumor samples are available from the primary tumor and/or from metastases, analyses will be also performed in both. Samples will be labeled according to its origin: diagnosis (primary tumor or metastasis) or baseline sample.

The expression levels and subcellular localization of selected molecules involved in different DNA repair mechanisms, such as nucleotide excision repair (e.g., XPG), homologous recombination repair (e.g., RAD51), among others, will be analyzed. Specifically, mRNA and protein from tumor samples will be subjected to quantitative reverse transcription polymerase chain reaction (qRT-PCR) and immunohistochemistry (IHC) in tissue microarrays (TMA), and immunofluorescence in whole tumor sections. The polymorphisms and mutational status of genes involved in DNA repair mechanisms or related to the mechanism of action of PM01183 or to the disease might also be analyzed, if relevant.

All PGx analyses will be performed in central reference laboratories selected by the Sponsors (see Study Contacts). Tissue blocks or sections will be shipped at room temperature to Pharma Mar S.A. who will coordinate the shipments and will cover all the costs. A manual describing the procedures for collection, shipping and handling of the samples will be provided as a separate document.

